C.3.7. Neuropsychological deficits among survivors of out-of-hospital cardiac arrest.

[figure not shown]

This NIH-funded (R01HD046442) prospective study determined the nature and severity of residual cognitive deficits for survivors of OHCA. Thirty OHCA patients who recovered alertness within 1-3 days of ROSC but remained confused at one week, and 30 non-OHCA coronary care admissions (matched controls) were administered neuropsychological testing at 90 days in five cognitive domains: memory, executive function, lexical-semantic, visuoperceptual, and psychomotor (**Figure 8**). Subjects fell into two deficit profiles. Two-thirds had only mild memory deficits and borderline psychomotor deficits compared to controls; 40% in this mild group had returned to work. The other one-third of patients had severe impairments in all domains. In the severe group, only as impairment in memory or psychomotor

domains increased did impairments in other domains appear. Follow-up evaluation at one year revealed discouraging little further cognitive improvement over the levels reached at 90 days. Only one additional subject returned to work. In addition, we assessed health-related quality of life (QOL) at one year using the Sickness Impact Profile-68 (SIP-68)⁴⁴, a measure of health-related functional status in rehabilitation medicine, and found that the OHCA patients reported more adverse effects on health than the cardiac control patients due to poorer psychological health and social participation, not due to effects on physical health.

The proposed study will use a similar methodology for neuropsychological testing and functional assessment at 180 days after resuscitation among survivors.

Figure 8: Composite z-scores – mean and standard deviation – for neuropsychological function in five cognitive domains among cardiac controls (CC), all out-of-hospital cardiac arrests (OHCA), and mild and severely impaired OHCA patients separately. Deficits after OHCA were most common and most severe in memory and psychomotor domains.

D.1. RESEARCH DESIGN AND METHODS

D.1.1 Specific Aims

We will test if a protocol for rapid FiO₂ optimization following ROSC from cardiac arrest is associated with:

- *Reduced in vivo oxidative stress during the post-resuscitation phase of therapy (Aim 1)*

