- *Reduced neurological disability at hospital discharge (Aim 2)*
- *Reduced neuropsychological and functional deficits among survivors at 180 days (Aim 3)*

D.1.2. Overview

Design: Prospective protocol implementation study with an observational comparison group [REOX II (intervention component) versus REOX I (observational component)]

Participants: Adult patients resuscitated from cardiac arrest

Enrollment location: Emergency Departments of 6 urban academic medical centers

Intervention: Implementation of a clinical protocol for rapid FiO₂ optimization after ROSC from cardiac arrest.

Primary outcome: Good neurological outcome (defined as Modified Rankin Scale ≤ 3 ⁴⁵ at hospital discharge).

Secondary outcomes: Neuropsychological tests and ability to return to work among survivors at 180 days.

Mechanistic outcomes: Oxidative stress markers (IsoPs/IsoFs) in plasma 0-6 hours after ROSC.

Estimated sample size and study duration: 280 patients (205 from REOX I and 75 from REOX II).

[figure not shown]
D.2. REOX II Study Protocol

Study setting and population: This study is the second phase in a two-phase study. The initial phase, REOX I, was an observational-only study. As in REOX I, REOX II will identify subjects with return of spontaneous circulation (ROSC) after cardiac arrest in 6 hospitals (Cooper University Hospital, Camden, NJ; Hospital of the University of Pennsylvania and Penn-Presbyterian Medical Center, both in Philadelphia, PA; University of Mississippi Medical Center, Jackson, MS; Methodist Hospital, Indianapolis, IN; and Beth Israel Deaconess Medical Center, Boston, MA). The inclusion criteria are: age > 17 years; cardiac arrest; ROSC achieved; comatose (Glasgow Coma Scale motor score < 6) after ROSC; and clinician intent to treat with target temperature management. The exclusion criteria are: presumed etiology of arrest is trauma, hemorrhage or sepsis; resident of a nursing home or other long-term care facility; known or clinically apparent pregnancy; known lack of commitment to aggressive support by next of kin; and any other condition, that, in the opinion of the investigator, would preclude the subject from being a suitable candidate (e.g. end stage chronic illness with no reasonable expectation of survival to hospital discharge).

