Patient identification and recruitment: Each of the participating centers currently has a mechanism in place for real-time notification of study personnel when an OHCA subject arrives in the emergency department (ED) or when a cardiac arrest occurs in-hospital. Each center has previously validated its notification mechanism to ensure that subjects will not be missed and the population of potentially eligible subjects will be consecutive cardiac arrest subjects. Study personnel will assess patient eligibility and will immediately enroll subjects meeting all inclusion and no exclusion criteria.

Informed consent: In line with REOX I (observational-only component), in REOX II we will begin initial collection of cardiac arrest and post-resuscitation data immediately after ROSC. As per the inclusion criteria all subjects will be comatose during the initial post-ROSC period and therefore will not be able to consent themselves for the study intervention (i.e. protocol for rapid FiO₂ optimization after cardiac arrest). Once a subject is identified to have all inclusion and no exclusion criteria, we will approach surrogates (i.e. next of kin or legally authorized representative)

Figure 9 Flow diagram for enrollment

[figure not shown]
within the first four hours after ROSC for written informed consent and HIPAA authorization prior to implementation of the study intervention. If communication with a surrogate within the first four hours after ROSC is not achieved the subject will not be eligible for the study intervention. However, for subjects who are excluded from the study intervention due to lack of informed consent within the first four hours after ROSC, we will approach subjects or surrogates at a later time for written informed consent and HIPAA authorization for participation in the observational only (REOX I) component of the study including (a) use of plasma samples for research purposes (both stored samples obtained at the time of initial resuscitation and new samples); (b) determination of Modified Rankin Scale at hospital discharge; and (c) follow-up visits for neuropsychological testing at 180 days (**Figure 9**).

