Therapeutic interventions: **Table 3** displays the standard elements of post-resuscitation care across all centers. All sites are experienced in target temperature management after ROSC and target 32-36°C for 24 hours using external cooling devices (Arctic Sun, Medivance, USA, or Gaymar III, Gaymar Industries, USA). Using a standardized order set for target temperature management induction, we demonstrated successful achievement of target temperature in 96% of patients and a median time from ROSC to target temperature of four hours (i.e. faster than the landmark randomized trial) in our routine clinical care.⁴⁰ All standard elements in **Table 3** reflect current AHA recommendations.¹² All subjects in this study will receive standard post-resuscitation care. Since none of the sites previously had a protocol in place for FiO₂ titration after ROSC and our standardized order sets for post-resuscitation care do not have orders for FiO₂ titration, subjects in REOX I (observational only component) had clinician-directed FiO₂ titration after ROSC.

For the interventional component of this study we will implement the protocol for rapid FiO₂ optimization after cardiac arrest (**Figure 10**) at all sites. Once a subject is identified and written informed consent is obtained from a surrogate, the study intervention (i.e. rapid FiO₂ optimization protocol) will be activated by the investigator who receives notification in real-time. (see “*Patient identification and recruitment*” above). The on call investigator will communicate directly with the clinical care team at the bedside and will ensure activation and adherence to the clinical protocol. Subjects enrolled in the study intervention will receive standard post-resuscitation care in **Table 3** *plus* rapid FiO₂ optimization according to **Figure 10**. Our sites have an outstanding track record of sustained clinical adherence to new resuscitation protocols for multi-year time periods.³⁷⁻⁴² Subjects who are excluded from the study intervention due to lack of informed consent within the first four hours after ROSC, will still be eligible for the observational only aspect of this study (REOX I). These subjects will receive standard post-resuscitation care outlined in **Table 3**, but will not have activation of the rapid FiO₂ optimization.

Table 3: Standard elements of post-cardiac arrest care across all centers. (TH = therapeutic hypothermia; GCS = Glasgow Coma Scale; ROSC = return of spontaneous circulation)

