Data collection: We will collect baseline data (e.g. demographics, comorbidities, etc.) and intra-arrest data (e.g. location, initial rhythm, length of downtime, etc.) using the Utstein template for cardiac arrest research⁴⁶ including the recommended variables for post-resuscitation research.⁴⁷ We will capture multiple indicators of post-resuscitation care quality in accordance with the 2010 AHA guidelines.¹² As mandated by the protocol (**Figure 10**) above, our standardized order set for post-resuscitation care will include multiple arterial blood gas (ABG) analyses for partial pressure of arterial oxygen (PaO_2) measurement after ROSC. As part of standard care each institution already obtains ABG analyses at 0- and 6-hours after ROSC. Any additional ABG analyses required to achieve the PaO_2 goal described in **Figure 10** will be considered for research purposes and will be funded by the study. We will record all ABG results over the initial 36 hours after ROSC. We will capture SaO_2 continuously for the initial 36 hours after ROSC. We will also capture every adjustment in FiO_2 from respiratory therapy records and the precise time of the adjustment. We will obtain plasma samples after ROSC at 0- and 6-hours after ROSC and ship the samples to the laboratory of our collaborator [name] (Vanderbilt) for measurement of isoprostanes (IsoPs) and isofurans (IsoFs) by gas chromatography negative ion chemical ionization mass spectrometry (GC/NICI/MS). IsoP and IsoF assays are remarkably stable and therefore are applicable to stored specimens. We can measure IsoPs and IsoFs on clinical plasma samples obtained immediately after ROSC because (after informed consent is secured) we can use samples left over in the clinical laboratory that are routinely discarded.

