Secondary analyses: We will compare proportions of good neurological outcome [defined as a mRS ≤ 3 (based on the preliminary data of our collaborator, [name], University of Pittsburgh)],⁴⁵ between subjects who receive the study intervention (i.e. rapid FiO₂ optimization) vs. those who do not receive the study intervention, using binomial test. Among survivors, we will compare the 180-day neuropsychological measures (composite z-scores for each cognitive domain) between the same two groups using t-test or Mann-Whitney U as appropriate with corrections for multiple comparisons. We will compare the proportions of patients able to return to work between the two groups using binomial test. We will compare plasma IsoPs/IsoFs at each time point between the two groups using t-test or Mann-Whitney U as appropriate with corrections for multiple comparisons.

Sample Size: The sample size calculation in the initial study proposal was based on the primary outcome, mRS at hospital discharge, and we planned to enroll a total of 266 subjects. To ensure adequate power to test the relationships between the above independent variables and cognitive domains, we assumed a medium relationship strength between the six independent variables and each of the five cognitive domains ($R^2 = 0.15$). In order to achieve 80% power and an $\alpha = 0.05$ we would require a minimal of 85 subjects to undergo neuropsychological testing at 180 days. This sample size will be among the largest prospective studies of

neuropsychological outcomes that we are aware of in the literature.^{8,29-32} Assuming a 15% drop out rate for lost to follow up for neuropsychological testing at 180 days we would require 98 subjects to be discharged with a mRS \leq 4. Based on preliminary data from REOX I we expect 35% of patients will be discharged with a mRS \leq 4 and undergo cognitive testing at 180 days. We would therefore require a minimal total sample size of 280 subjects between REOX I and II combined for the multivariable testing. We have enrolled 200 subjects in REOX I to date. We anticipate additional subjects to be enrolled in REOX I and therefore plan for 75 subjects to be enrolled in REOX II to ensure a total sample size of at least 280 subjects.

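### The only planned test of Aim 1 compares 6-hour isoprostanes and isofurans between non-randomised groups without using each patient's own 0-hour value

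*Combined protocol and SAP*

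**What the plan says.** Section D.1.1 lists as the first aim "Reduced in vivo oxidative stress during the post-resuscitation phase of therapy (Aim 1"). Section D.1.2 describes the design as a "Prospective protocol implementation study with an observational comparison group" and plans 205 patients from REOX I and 75 from REOX II. It lists plasma isoprostanes and isofurans (IsoPs/IsoFs) over 0–6 hours as the mechanistic outcomes.

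On sampling, D.2 Data collection says: "We will obtain plasma samples after ROSC at 0- and 6-hours after ROSC". Plasma left over from clinical samples taken right after ROSC may be used.

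On the start of the protocol, D.2 Informed consent says surrogates are approached "within the first four hours after ROSC for written informed consent and HIPAA authorization prior to implementation of the study intervention". D.2 Therapeutic interventions agrees: "Once a subject is identified and written informed consent is obtained from a surrogate, the study intervention" is activated. Consent for the observational component is sought later "for subjects who are excluded from the study intervention due to lack of informed consent within the first four hours after ROSC".

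On analysis, Secondary analyses says: "We will compare plasma IsoPs/IsoFs at each time point between the two groups using t-test or Mann-Whitney U as appropriate", with a multiplicity correction whose method is not named. The multivariable models in the Analysis section have mRS and the five cognitive domains as outcomes. No change score, baseline-adjusted model or repeated-measures model is given for the markers.

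**The concern.** Only the 6-hour comparison can show a protocol effect, because activation follows consent and the 0-hour sample precedes it. Yet the 6-hour comparison is a plain two-group test.

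Membership of the groups depends on study phase (200 observational patients were already enrolled when the plan was written) and on whether a surrogate consented within four hours. Neither mechanism balances oxidative stress at 0 hours. The plan accepts the need to adjust for prognosis when it models mRS and cognition, but gives Aim 1 no such protection.

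The separate 0-hour comparison may reveal an imbalance. It does not correct the 6-hour result for one. At stake is the mechanistic conclusion that the protocol reduces oxidative stress, together with precision that the trial has already paid for by assaying both samples.

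**Working it through.** **The plan's own figure.** There is none for Aim 1. The Sample Size paragraph covers the cognitive models only, and its chain reproduces: an omnibus F test with R² = 0.15, six predictors, 80% power and alpha 0.05 needs 84 patients (power 80.8% at the stated 85); 85 × 1.15 = 97.75, so 98; 98 / 0.35 = 280.

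**Inputs.** From D.1.2: 205 and 75 patients. Assumed, because the documents are silent: SD of 1 at both times; 0–6 hour correlation ρ of 0.3, 0.5 or 0.7; effect of 0.35 or 0.25 SD; 0-hour imbalance d₀ of 0.3 or 0.1 SD; two-sided alpha 0.05 / 2 = 0.025 (two markers at 6 hours), critical value 2.241; complete pairs.

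**Standard errors.** Unadjusted: √(1/205 + 1/75) = 0.135 SD. Adjusted for the 0-hour value: 0.135 × √(1 − ρ²).

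**Power** = Φ(effect/SE − 2.241):

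| Effect | Unadjusted | ρ = 0.3 | ρ = 0.5 | ρ = 0.7 |
|---|---|---|---|---|
| 0.35 SD | 64% | 68% | 77% | 92% |
| 0.25 SD | 35% | 38% | 46% | 64% |

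**False positives.** Let δ be the part of the imbalance still present at 6 hours. With no true effect, the unadjusted bias is δ and the adjusted bias is δ − ρd₀. The rejection rate is 1 − Φ(2.241 − bias/SE) + Φ(−2.241 − bias/SE). For d₀ = 0.3 and ρ = 0.3, 0.5, 0.7:

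| What happens by 6 hours | Unadjusted bias | Unadjusted rejects | Adjusted bias (size) | Adjusted rejects |
|---|---|---|---|---|
| Regresses like individual values (δ = ρd₀) | 0.09, 0.15, 0.21 | 6%, 13%, 25% | 0 | about 2.5% |
| Persists in full (δ = d₀) | 0.30 | 49% | 0.21, 0.15, 0.09 | 27%, 17%, 10% |
| Vanishes (δ = 0) | 0 | 2.5% | 0.09, 0.15, 0.21 | 6%, 17%, 48% |

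A simulation of 6,000 trials per setting agreed for the first two rows: regressing, unadjusted 5.9%, 12.8%, 23.6% and adjusted 2.5%, 2.6%, 2.5%; persisting, unadjusted 48% to 50% and adjusted 26.5%, 16.2%, 9.2%.

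For d₀ = 0.1 the stakes are small: regressing, 3% to 4.5% against 2.5%; persisting, 7% against 5%, 4% or 3%.

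Adjustment shrinks the bias whenever |δ − ρd₀| < |δ|, that is, when δ exceeds ρd₀/2. At ρ = 0.5 and d₀ = 0.3 that is 0.075 SD, a quarter of the 0-hour difference.

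**Can the 0-hour test serve as a safeguard?** Its power to detect a 0.3 SD imbalance is 60% at alpha 0.05, and 39% at 0.0125 (0.05 / 4, if the correction spans two markers at two times). A non-significant result would not rule out a material imbalance.

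**Missing 0-hour samples.** If 20% lack only that sample, complete pairs number 164 and 60, and the unadjusted SE on those pairs would be 0.151. Adjusted power for 0.35 SD is then 58%, 67% or 84%, against 64% unadjusted in all 280. Break-even is at 1 − ρ² = 0.8, so ρ = √0.2 = 0.45. If the 6-hour sample is the missing one, unadjusted power is 53% and adjustment still gains.

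**The case against.** The strongest objection is that adjustment is not always the less biased choice. Section C.3.5 says that marker formation depends on ambient oxygen, and A.3 says that high FiO₂ is kept up for widely varying periods after ROSC. A 0-hour difference could therefore be a transient trace of early oxygen exposure. If a 0.3 SD difference has gone by 6 hours, the adjusted test over-corrects and rejects up to 48% of the time, against 2.5% for the planned test. This stands as a possibility. It is the reason to keep the unadjusted comparison as a sensitivity analysis, but it requires nearly all of the imbalance to disappear.

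Other points bear on size. Effect, correlation and imbalance are all assumed. At ρ = 0.3 the power gain is only four points. With alpha 0.0125 the unadjusted rates for a 0.3 SD imbalance fall to 3%, 8% and 17% (regressing) and 39% (persisting). These change the size of the illustration, not the gap in the plan.

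It is also fair to say that the 0-hour comparison is pre-specified, that these are mechanistic outcomes under Secondary analyses, and that the other between-group tests there are equally unadjusted. But this is the only stated test of a named Specific Aim, and here a pre-activation measurement of the outcome itself is already planned. Finally, baseline adjustment leaves differences of study phase and consent selection that do not act through the 0-hour level. That is correct and has to be stated in the report.

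**Conclusion.** The concern holds. The plan's one test of Aim 1 leaves out a baseline measurement that the trial already collects, in a comparison that is not randomised.

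The size cannot be fixed from the documents. With a 0-hour imbalance near 0.1 SD little is at stake. Near 0.3 SD the unadjusted test's false-positive rate is 6% to 49% against a nominal 2.5%, unless the imbalance has vanished by 6 hours. Adjustment lowers that rate both where the imbalance regresses and where it persists, without always restoring 2.5%. With no imbalance at all the gain is precision, equal to a factor of √(1 − ρ²) on the standard error.

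These figures rest on normal approximations, equal SDs at both times, complete pairs and a correction over two markers. The change is worth making, but it concerns a mechanistic outcome only.

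**What to change.** For each marker, define the Aim 1 test as a regression of the 6-hour level on group and the patient's own 0-hour level, plus the Analysis-section covariates fixed before activation: Charlson index, downtime, initial rhythm and arrest location. A change score is not a substitute, because under a regressing imbalance it keeps a bias of (ρ − 1)d₀, which is −0.15 SD at ρ = 0.5 and d₀ = 0.3.

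The SAP should also:

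- set the scale (transformation or ranks) by a rule that does not look at group differences;
- apply the promised correction, with its method named, to the two markers at 6 hours, and report 0-hour levels descriptively;
- name a method for imputing missing 0-hour values;
- not impute 6-hour levels for patients who die before 6 hours, but report those deaths by group;
- keep the unadjusted 6-hour comparison as a sensitivity analysis;
- state that adjustment does not remove all confounding between the groups.

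The cost is SAP wording. Both samples and all four covariates are already planned, so no visit, assay or patient is added. The two downsides are lost power if many 0-hour samples are missing and only complete pairs are used, and over-correction if an imbalance has vanished by 6 hours. The imputation and the sensitivity analysis address them.

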[name] and his laboratory were the investigators who discovered **isofurans** (IsoFs), which are isomeric products of lipid peroxidation characterized by a substituted tetrahydrofuran ring. Isofuran assays are essential for the proposed study. Under conditions of increasing ambient oxygen concentrations (e.g. high FiO₂ producing supranormal PaO₂) an oxygen molecule is added to the carbon-centered radical to yield a peroxy radical, and this favors the production of IsoFs instead of IsoPs (Figure 7). These reactions are competing, mutually exclusive, and **differentially regulated by the ambient oxygen concentration**. Although IsoPs are an excellent assessment of oxidative stress in general, under hyperoxic conditions measurement of IsoPs alone would underestimate the extent of lipid peroxidation. A complete picture across all FiO₂ concentrations is only possible with measurement of **both IsoPs and IsoFs**. Given that IsoFs are a remarkably sensitive indicator of hyperoxia-induced oxidative injury, and the proposed study is focused on hyperoxia exposure, measuring IsoFs in addition to IsoPs in this study is vital. Importantly, and pertinent to the feasibility of the proposed study, IsoF and IsoP assays are remarkably stable and therefore are applicable to stored specimens. In addition, IsoFs and IsoPs are quantified in the same GC/NICI/MS assay using a single purification protocol, allowing for maximum analytical simplicity. We will measure plasma IsoPs and IsoFs in this study.

Figure 7: Differential effects on isofuran and isoprostane formation by ambient oxygen. Excessive ambient oxygen favors isofurans.

C.3.6. Association between isofuran levels after resuscitation and clinical outcome.

Roberts LJ, et al. Preterm resuscitation with low oxygen causes less oxidative stress, inflammation, and chronic lung disease. *Pediatrics* 2009;124(3):e439-49.

In this clinical trial comparing resuscitation with 90% FiO₂ versus 30% FiO₂ at the time of delivery among extremely low gestational age neonates, [name] and colleagues assessed *in vivo* oxidative stress by measuring urine isofurans by GC/NICI/MS. They found that neonates resuscitated with 30% FiO₂ had significantly lower isofuran levels over the first day after resuscitation compared to those resuscitated with 90% FiO₂, and with this reduction in isofurans, neonates in the 30% FiO₂ arm also had improved clinical outcomes (reduction in acute lung injury and bronchopulmonary dysplasia).

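### Aim 1 has no combined isoprostane-isofuran measure, so a fall in isofurans could reflect an oxygen-driven shift between the two markers

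*Combined protocol and SAP*

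**What the plan says.** All references are to the combined protocol and SAP.

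- D.1.1 (Specific Aims) states Aim 1 as a reduction in oxidative stress in vivo after resuscitation. It names no marker and no decision rule.
- D.1.2 (Overview) gives the mechanistic outcome as "Oxidative stress markers (IsoPs/IsoFs) in plasma 0-6 hours after ROSC".
- D.2, Secondary analyses, sets out the comparison: "We will compare plasma IsoPs/IsoFs at each time point between the two groups using t-test or Mann-Whitney U as appropriate". A multiplicity correction is to be applied, but its method is not stated, and neither are the sidedness, a lead marker, or a sum, ratio or joint test.
- D.2, Data collection, sets plasma sampling at 0 and 6 hours after ROSC.
- C.3.5 explains the chemistry: "These reactions are competing, mutually exclusive, and differentially regulated by the ambient oxygen concentration". It warns that "under hyperoxic conditions measurement of IsoPs alone would underestimate the extent of lipid peroxidation". Its stated remedy is to assay the two markers together. It also says that one assay with one purification step quantifies both.

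**The concern.** The intervention targets a PaO₂ of 60-99 mmHg (C.3.3), against clinician-directed titration in the comparison group (D.2, Therapeutic interventions). It is therefore meant to change the very quantity that, by C.3.5, decides whether a radical ends as IsoF or IsoP. Lower oxygen should reduce the IsoF share even if the amount of peroxidation stays the same.

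The plan measures both markers to obtain a full picture, but the analysis section never puts the two together. A lower IsoF could then be reported as support for Aim 1 when it shows mainly that PaO₂ fell. The opposite error is also possible: a real reduction in peroxidation could leave IsoP flat because the shift offsets it. In either case the trial's mechanistic claim would rest on post hoc interpretation of two markers that may move in opposite directions.

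**Working it through.** **The plan's own figure.** No effect size, variability or power is stated for Aim 1. The total of 280 comes from the cognitive-domain regression (85 × 1.15 ≈ 98; 98 / 0.35 = 280). It reproduces but does not bear on this point.

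**Arithmetic of a pure shift.** Let T be the combined amount and q the IsoF share, so IsoF = qT and IsoP = (1 − q)T. Hold T at 1 and move q from 0.50 to 0.40:
- IsoF: 0.50 to 0.40, a fall of 20%
- IsoP: 0.50 to 0.60, a rise of 20%
- Sum: 1.00 to 1.00, no change

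**The opposite error.** Let T fall by 15% while q moves from 0.50 to 0.40:
- IsoP: 0.50 to 0.85 × 0.60 = 0.51, so the marker shows no improvement
- IsoF: 0.50 to 0.85 × 0.40 = 0.34, which overstates a 15% reduction as 32%

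**How often the planned tests would show this.** Group sizes (205 and 75) are from D.1.2. The rest is assumed:
- T is log-normal with CV 50% and the same distribution in both groups.
- q is logit-normal with SD 0.5, and the markers add on a common scale.
- Two-sided t-tests are run on log values at one post-baseline time.
- Each marker is tested at 0.05 / 4 = 0.0125 (two markers at two times, Bonferroni). The sum is tested at two-sided 0.05.
- Each scenario has 1,500 simulated trials.

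| IsoF share, control → intervention | True change IsoF / IsoP | IsoF significantly lower | IsoP significantly higher | IsoF lower, IsoP not significantly changed | Sum significantly lower |
|---|---|---|---|---|---|
| 50% → 50% | 0 / 0 | 0.7% | 0.9% | 0.5% | 2.5% |
| 50% → 45% | −10% / +10% | 14.2% | 10.5% | 14.1% | 1.7% |
| 60% → 50% | −16.7% / +25% | 52.3% | 68.6% | 24.3% | 2.8% |
| 50% → 40% | −20% / +20% | 72.0% | 49.9% | 44.5% | 2.3% |
| 20% → 15% | −25% / +6.25% | 80.8% | 6.0% | 79.3% | 2.9% |
| 30% → 20% | −33.3% / +14.3% | 99.3% | 33.2% | 66.7% | 2.7% |

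The sum is tested at a looser threshold than the markers, yet it stays near its nominal one-directional rate of 2.5%. At 0.0125 its two-sided rejection rate is about 1%. Multiplicity correction does not help, because the IsoF fall is a real difference and not a chance finding.

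**What the sum costs and gains.** Suppose IsoF falls by 25% and IsoP does not change. The sum then falls by only 0.25 × share: 12.5%, 7.5% or 5% at IsoF shares of 50%, 30% or 20%. With a narrower spread of q (logit SD 0.3), IsoF alone detects this in about 91% to 97% of trials and the sum (at 0.05) in about 13% to 53%. If both markers fall by 20% with no shift, the sum detects it in 93.1% (at 0.05), against 74.5% for IsoF and 73.3% for IsoP (each at 0.0125).

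**The case against.** A reader might infer that the plan will declare Aim 1 met on IsoF alone. The documents do not say so. Both markers are carried through sampling, outcome and analysis, and a large shift would be visible. When the share falls from 50% to 35% (logit SD 0.3), about 91% to 93% of simulated trials show IsoF significantly lower together with IsoP significantly higher. This stands for large shifts. It does not cover the others: in the table, IsoF falls without a significant change in IsoP in 14% to 79% of trials, so the warning sign is often absent.

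A reader might also infer that a lower IsoF is no evidence of benefit. That goes too far. A.3 postulates that hyperoxia increases reactive oxygen species and lipid oxidation, so less oxygen may reduce total formation and IsoPs need not rise. C.3.5 presents IsoFs as a sensitive index of hyperoxic injury, and C.3.6 describes a neonatal trial in which lower isofurans accompanied better outcomes. A pure shift is one possibility among several. The planned tests simply cannot tell them apart.

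It is tempting to replace the separate tests with the sum. The sensitivity figures argue against that, and the documents do not show that IsoF + IsoP captures all lipid peroxidation.

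The size of any shift at 6 hours is also unknown. Consent may come up to four hours after ROSC (D.2, Informed consent), which leaves some patients as little as 6 − 4 = 2 hours on protocol before the sample.

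Finally, separate testing is the natural reading of the slash in the analysis sentence, but it is not explicit. If a ratio were meant, it would measure only the shift.

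**Conclusion.** The point holds as a gap in how Aim 1 will be read. By the plan's own chemistry the intervention can move the balance between the markers. The analysis has no combined measure and no rule for opposite results, so a lower IsoF could be taken as reduced oxidative stress when it partly or wholly reflects a shift. Under the assumptions above, a shift with no change in total gives a significant IsoF fall in 14% to 99% of trials and a significant fall in the sum in about 2% to 3%. The IsoF share, its spread, the CV, additivity and the Bonferroni divisor are all assumed, so these are illustrations and not estimates for this trial. The outcome is mechanistic and the analysis is listed as secondary, so this is a cheap improvement and not a flaw that threatens the primary result.

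**What to change.** In D.1.2 and in D.2, Secondary analyses:

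1. Keep the separate IsoF and IsoP comparisons.
2. Add a prespecified between-group comparison at 6 hours of a combined peroxidation measure: IsoF + IsoP in common units, or a standardised sum so that the more abundant marker does not dominate. State which, and why. The choice matters. In the 20% → 15% row, a pure shift lowers IsoF by 25% and raises IsoP by only 6.25%, so a standardised sum can fall although the total has not. The sum in common units does not have this problem.
3. Add the IsoF:IsoP ratio at 6 hours as the marker of shift.
4. Base the Aim 1 conclusion on the joint pattern. Report lower IsoF with higher IsoP and no lower combined measure as a shift, not as reduced total oxidative stress. Report lower IsoF with no clear change in either IsoP or the combined measure as unresolved, with confidence intervals for all measures.

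Six hours is the informative time, because consent and activation follow ROSC and the 0-hour sample can hardly reflect the intervention.

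Cost: wording only, since the same assay yields every quantity. Two added comparisons take the count from four to six, which under Bonferroni moves the per-test level from 0.0125 to 0.05 / 6 = 0.0083. The combined measure is less sensitive than IsoF when only IsoF falls, which is why the separate comparisons should stay.
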